7.1.5.2 Treatment Period

IV study therapy should be administered for a minimum of 5 full days for subjects with cIAI or cUTI or 7 full days for subjects with HABP/VABP. This translates to either 20 (cIAI, cUTI) or 28 (HABP/VABP) dose of IMI-containing therapy based on the q6h dosing regimen. This also translates to either 10 (cIAI, cUTI) or 14 (HABP/VABP) doses of CMS/placebo to CMS. The total duration of IV study therapy should not exceed 21 days. Duration of study therapy longer than 21 days must be approved by the Sponsor.

7.1.5.3 Post-Therapy

An EFU (Day 5 to 9 post-therapy) and a Day 28 post-randomization visit must be completed for each subject. Depending on the total duration of IV study therapy, the EFU and Day 28 post-randomization visit may be combined into a single visit. These visits may only be combined as long as compliance with the protocol-specified visit windows is maintained for both visits. Specifically, if a subject receives 17 to 21 days of IV study therapy, the EFU visit may potentially be combined with the Day 28 visit. For example, if 17 days of IV therapy are provided, the EFU visit could be scheduled 11 days (9+2) following completion of therapy which would be 28 days (17 days of IV therapy +11 days of follow-up) following randomization. It is required that for any case, the allowable visit window ranges are maintained and all procedures required for each visit must be completed for the combined visit. For durations of study therapy longer than 21 days, combining visits should be discussed with the Sponsor.

A Safety Follow-Up Visit (Day 14 post-therapy) is required if the Day 28 (+3 day-window) post-randomization visit occurs prior to 14 days following EOT. In order to obtain a full 14 days of safety follow-up following EOT, subjects who receive ≥ 18 days of therapy would require this Safety Follow-Up Visit since $18 + 14$ would be outside of the window for the Day 28 visit.

7.2 Assessing and Recording Adverse Events

An adverse event is defined as any untoward medical occurrence in a patient or clinical investigation subject administered a pharmaceutical product and which does not necessarily have to have a causal relationship with this treatment. An adverse event can therefore be any unfavourable and unintended sign (including an abnormal laboratory finding, for example), symptom, or disease temporally associated with the use of a medicinal product or protocol-specified procedure, whether or not considered related to the medicinal product or protocol-specified procedure. Any worsening (i.e., any clinically significant adverse change in

frequency and/or intensity) of a preexisting condition that is temporally associated with the use of the Sponsor's product, is also an adverse event.

Changes resulting from normal growth and development that do not vary significantly in frequency or severity from expected levels are not to be considered adverse events. Examples of this may include, but are not limited to, teething, typical crying in infants and children and onset of menses or menopause occurring at a physiologically appropriate time.

Sponsor's product includes any pharmaceutical product, biological product, device, diagnostic agent or protocol-specified procedure, whether investigational (including placebo or active comparator medication) or marketed, manufactured by, licensed by, provided by or distributed by the Sponsor for human use.

Adverse events may occur during clinical trials, or as prescribed in clinical practice, from overdose (whether accidental or intentional), from abuse and from withdrawal.

All adverse events that occur after the consent form is signed but before randomization must be reported by the investigator if they cause the subject to be excluded from the trial, or are the result of a protocol-specified intervention, including but not limited to washout or discontinuation of usual therapy, diet, placebo treatment or a procedure. From the time of randomization through 14 days following cessation of treatment, all adverse events must be reported by the investigator. Such events will be recorded at each examination on the Adverse Event case report forms/worksheets. The reporting timeframe for adverse events meeting any serious criteria is described in section 7.2.3.1. The investigator will make every attempt to follow all subjects with non-serious adverse events for outcome.

Electronic reporting procedures can be found in the EDC data entry guidelines. Paper reporting procedures can be found in the Investigator Trial File Binder (or equivalent).

7.2.1 Definition of an Overdose for This Protocol and Reporting of Overdose to the Sponsor

In this trial, an overdose in study therapy is defined as administration of a total daily dose of IMI/REL in excess of 4 g (IMI) + 2 g (REL) OR a total daily dose of IMI in excess of 4 g per day OR a total daily dose of CMS in excess of the protocol-specified doses in Section 5.2.1.1, [Table 12](#).

If an adverse event(s) is associated with ("results from") the overdose of Sponsor's product or vaccine, the adverse event(s) is reported as a serious adverse event, even if no other seriousness criteria are met.

If a dose of Sponsor's product or vaccine meeting the protocol definition of overdose is taken without any associated clinical symptoms or abnormal laboratory results, the overdose is reported as a non-serious Event of Clinical Interest (ECI), using the terminology "accidental or intentional overdose without adverse effect."

All reports of overdose with and without an adverse event must be reported by the investigator within 24 hours to the Sponsor either by electronic media or paper. Electronic reporting procedures can be found in the EDC data entry guidelines. Paper reporting procedures can be found in the Investigator Trial File Binder (or equivalent).

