3.2 Secondary Objective(s) & Hypothesis(es)

3.2.1 Key Secondary Objectives

- (1) Objective: To estimate the proportion of subjects with a favorable clinical response to IMI/REL (Treatment Group 1 only) and CMS + IMI (Treatment Group 2) at Day 28 post-randomization.
- (2) Objective: To estimate the incidence of all-cause mortality through Day 28 post-randomization in Treatment Group 1 (IMI/REL) and in Treatment Group 2 (CMS + IMI).
- (3) Objective: To estimate the proportion of subjects who experience treatment-emergent nephrotoxicity in Treatment Group 1 (IMI/REL) and in Treatment Group 2 (CMS + IMI).

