NOTE: In subjects in whom fatigue, nausea, vomiting, and right upper quadrant pain or tenderness was a part of the subject's presenting illness, the subject may continue on therapy if there is no elevation in transaminases from baseline measurements. In such subjects who experience a return of their original symptoms with accompanying elevations in transaminases it may be difficult to determine the cause, and investigators may discuss subjects in this situation with the Sponsor Clinical Director prior to discontinuation, if desired.

In subjects with preexisting transaminase elevations,

- Further increase in transaminases to ≥ 8 X ULN [with at least 50% increase from transaminase values collected at randomization (Day 1)] that is not anticipated from their underlying medical condition.
- ALT or AST ≥ 3 X ULN and new onset of clinical signs and symptoms of fatigue, nausea, vomiting, right upper quadrant pain or tenderness, fever (defined as body temperature $\geq 38.0^{\circ}\text{C}$ [$\geq 100.4^{\circ}\text{F}$]), rash, and/or eosinophilia ($> 5\%$)
- Clinically significant worsening of liver function associated with further transaminase elevations in a subject with abnormal transaminase levels already meeting the above criteria (i.e., ≥ 8 X ULN; ALT or AST ≥ 3 X ULN and new onset of clinical signs and symptoms listed) at baseline.

The subject will discontinue from study therapy, but will continue to participate in the study and will be assessed according to all study planned study procedures through the final study visit and will be evaluated for blood chemistry and hematology (including, at minimum, ALT, AST, alkaline phosphatase, bilirubin (direct + indirect) and creatine phosphokinase) until values return to within normal range. The trial site guidance for assessment and follow up of liver function test (LFT) elevations can be found in the Investigator Trial File Binder.

2. A post-baseline decline in estimated or actual creatinine clearance to a value of less than 15 mL/min.
3. The subject requires initiation of hemodialysis or peritoneal dialysis.
4. The subject has a confirmed positive serum or urine (sensitivity of < 25 million IU/L is required if using urine test) pregnancy test.
5. A physician investigator feels it is in best interest of the subject to discontinue for any reason, including, but not limited to, the need for alternative non-study antibacterial therapy.

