- ^d The details of any primary or secondary infection-site diagnoses (HABP/VABP, cIAI and/or cUTI) will be documented separately on the appropriate eCRF(s). Details should include the diagnosis and an additional diagnostic details associated with the infection site (e.g., characterization of the complicated nature of the cIAI and/or cUTI).
- ^e For the purpose of monitoring renal function during IV treatment, the most recently collected creatinine clearance should also be reported to IVRS daily to support dosage determination. (refer to Table 11 and Table 12 in Section 5.2.1.1). Any local or central laboratory abnormalities in serum creatinine that result in an adverse event or a dose adjustment.
- ^f Vital signs should be performed and documented on the appropriate electronic case report forms (eCRFs) at the randomization visit (Day 1) prior to administration of the first dose of study therapy and daily during IV study therapy. Vital signs should also be performed and documented at the additional visits specified.
- ^g Enter weight if a clinically significant weight change occurred and resulted in a change in CrCl category.
- ^h Monitor for adverse events and local infusion tolerability and collect infection-specific clinical signs and symptoms daily during IV study therapy and adverse experiences for 14 days after completion of IV study therapy. Laboratory abnormalities that emerge during IV therapy and are considered adverse experiences by the investigator must be followed until resolved or stabilized. Serious adverse experiences that are considered by the investigator to be possibly, probably or definitely related to the investigational product that is brought to the attention of the investigator at any time outside of 14 days post-therapy also must be reported immediately to the Sponsor.
- ⁱ Clinical signs and symptoms, radiographic (daily reporting not required for radiographic findings) and laboratory characteristics associated with the primary bacterial infection and any secondary bacterial infection sites (see Table 13) will be reviewed and documented on the appropriate electronic case report forms (eCRFs) daily during IV study therapy and at the additional visits specified.

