7.1.2.6 Adverse Event Monitoring

Clinical adverse events will be collected from the time of initiation of the first dose of IV study therapy through 14 days following completion of all IV study therapy. In addition, local infusion site tolerability will be evaluated daily during IV study therapy. The tolerability of all study therapy at the local IV infusion site will be based on investigator inspection and subject comments regarding signs and symptoms of intolerance. The IV infusion site should be observed daily during IV therapy to determine the presence/absence of erythema, induration, pain, tenderness, warmth, swelling, ulceration, local phlebitis, rash, or other reactions. All adverse events should be documented on the appropriate eCRF.

Laboratory adverse experiences will be based on safety laboratory tests (both central and local results), including hematology and chemistry tests from blood and urinalysis from urine. Please refer to Section 7.1.3 and 6.0 for more details on type of tests and timing of collection.

Please refer to Section 7.2 for details regarding assessment and documentation of adverse events.

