7.2.3 Immediate Reporting of Adverse Events to the Sponsor

7.2.3.1 Serious Adverse Events

A serious adverse event is any adverse event occurring at any dose or during any use of Sponsor's product that:

- Results in death;
- Is life threatening;
- Results in persistent or significant disability/incapacity;
- Results in or prolongs an existing inpatient hospitalization;
- Is a congenital anomaly/birth defect;
- Is an other important medical event

Note: In addition to the above criteria, adverse events meeting either of the below criteria, although not serious per ICH definition, are reportable to the Sponsor in the same timeframe as SAEs to meet certain local requirements. Therefore, these events are considered serious by the Sponsor for collection purposes.

- Is a cancer;
- Is associated with an overdose.

Refer to [Table 15](#) for additional details regarding each of the above criteria.

For the time period beginning when the consent form is signed until randomization, any serious adverse event, or follow up to a serious adverse event, including death due to any cause, that occurs to any subject must be reported within 24 hours to the Sponsor if it causes the subject to be excluded from the trial, or is the result of a protocol-specified intervention,

including but not limited to washout or discontinuation of usual therapy, diet, placebo treatment or a procedure.

For the time period beginning at randomization through 14 days following cessation of treatment, any serious adverse event, or follow up to a serious adverse event, including death due to any cause, whether or not related to the Sponsor's product, must be reported within 24 hours to the Sponsor either by electronic media or paper. Electronic reporting procedures can be found in the EDC data entry guidelines. Paper reporting procedures can be found in the Investigator Trial File Binder (or equivalent).

Additionally, any serious adverse event, considered by an investigator who is a qualified physician to be related to the Sponsor's product that is brought to the attention of the investigator at any time outside of the time period specified in the previous paragraph also must be reported immediately to the Sponsor.

All subjects with serious adverse events must be followed up for outcome.

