7.2.3.2 Events of Clinical Interest

Selected non-serious and serious adverse events are also known as Events of Clinical Interest (ECI) and must be reported to the Sponsor.

For the time period beginning when the consent form is signed until randomization, any ECI, or follow up to an ECI, that occurs to any subject must be reported within 24 hours to the Sponsor if it causes the subject to be excluded from the trial, or is the result of a protocol-specified intervention, including but not limited to washout or discontinuation of usual therapy, diet, placebo treatment or a procedure.

For the time period beginning at randomization through 14 days following cessation of treatment, any ECI, or follow up to an ECI, whether or not related to the Sponsor's product, must be reported within 24 hours to the Sponsor, either by electronic media or paper. Electronic reporting procedures can be found in the EDC data entry guidelines. Paper reporting procedures can be found in the Investigator Trial File Binder (or equivalent).

Events of clinical interest for this trial include:

1. an overdose of Sponsor's product, as defined in Section 7.2.1 - Definition of an Overdose for This Protocol and Reporting of Overdose to the Sponsor, that is not associated with clinical symptoms or abnormal laboratory results.
2. post baseline laboratory test values that meet the following criteria: an elevated AST or ALT lab value that is greater than or equal to 3X the upper limit of normal and an elevated total bilirubin lab value that is greater than or equal to 2X the upper limit of normal and, at the same time, an alkaline phosphatase lab value that is less than 2X the upper limit of normal, as determined by way of protocol-specified laboratory testing or unscheduled laboratory testing.*

*Note: These criteria are based upon available regulatory guidance documents. The purpose of the criteria is to specify a threshold of abnormal hepatic tests that may require an additional evaluation for an underlying etiology. The trial site guidance for assessment and follow up of these criteria can be found in the Investigator Trial File Binder.

3. a confirmed (i.e., verified by repeat testing) elevated AST or ALT laboratory value that is greater than or equal to $5 \times \text{ULN}$ as a result of within-protocol-specific testing or unscheduled testing.

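### AE, SAE and ECI collection stops 14 days after the last dose, so courses shorter than 14 days leave an uncollected stretch before the Day 28 visit scheduled for every subject

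*Combined protocol and SAP*

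**What the plan says.** Section 7.2 requires: "From the time of randomization through 14 days following cessation of treatment, all adverse events must be reported by the investigator". Section 7.2.3.1 applies the same close to SAEs, deaths from any cause included ("For the time period beginning at randomization through 14 days following cessation of treatment, any serious adverse event"), and Section 7.2.3.2 applies it to events of clinical interest ("For the time period beginning at randomization through 14 days following cessation of treatment, any ECI, or follow up to an ECI"). Section 7.1.2.6 begins at first dose rather than randomisation but ends at the same point: "Clinical adverse events will be collected from the time of initiation of the first dose of IV study therapy through 14 days" after therapy is completed. Footnote h of the flow chart in Section 6.0 likewise asks for "adverse experiences for 14 days after completion of IV study therapy".

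There is one exception. Under Section 7.2.3.1 an SAE that a physician investigator judges related must be reported even if it is one "that is brought to the attention of the investigator at any time outside of the time period specified". Footnote h repeats this.

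Other sections run to Day 28:

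- Section 6.0 schedules a Day 28 visit (+3 days) for every subject, with AE review, directed examination, hematology and chemistry. Section 7.1.4.1 keeps subjects who stop therapy early in all remaining visits.
- A key secondary objective in Section 3.2.1 is "To estimate the incidence of all-cause mortality through Day 28 post-randomization". Section 7.1.3.5.3 records survival status, with date and cause of death.
- Section 5.8 lists grounds for permanently stopping IV therapy. They include "A post-baseline decline in estimated or actual creatinine clearance to a value of less than 15 mL/min", a need for dialysis, and liver criteria.
- Section 8.2.5.2 compares the percentages of subjects with events between Groups 1 and 2, using the unstratified Miettinen and Nurminen method. It names no end to the AE analysis period and makes no allowance for length of follow-up.

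**The concern.** Safety and tolerability of IMI/REL is a primary objective (Section 3.1). Counted from randomisation, the period over which a subject can contribute an AE depends on how long that subject was treated, and duration is a post-randomisation variable that toxicity can cut short. Renal toxicity is the stated concern for the colistin arm (Section 4.2.3.2), so a difference in duration between arms is plausible, in a direction that cannot be known beforehand. Section 8.1.1 commits to assessing the effect of duration on treatment comparisons, but it does so within the efficacy analysis. The safety methods have no counterpart.

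Subjects on short courses are also seen and bled at Day 28, after their reporting window has closed. A new event found there need not enter the AE data. A death at that stage, judged unrelated and with no preceding SAE, counts in the mortality endpoint without being a required SAE. With planned evaluable groups of 30 and 15, and Tier 2 membership turning on four subjects, a few records can matter.

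**Working it through.** **Inputs.** Close of collection: last dose + 14 days (Sections 7.1.2.6, 7.2, 7.2.3.1, 7.2.3.2; footnote h). Day 28 visit: Day 28 to 31 (Sections 2.2 and 6.0). Minimum course: 5 days for cIAI and cUTI, 7 days for HABP/VABP. Usual maximum: 21 days (Section 7.1.2.1). Days are added as elapsed days, as the protocol does in 17 + 11 = 28 (Section 7.1.5.3).

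**The plan's own figures first.** Section 7.1.5.3 requires a safety follow-up visit from 18 days of therapy. With D days of therapy the window closes at D + 14. 17 + 14 = 31 still fits the Day 28 (+3) window and 18 + 14 = 32 does not, so 18 is reproduced. The maximum participation of 35 days is 21 + 14.

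**Uncollected time before Day 28** = max(0, 28 − (D + 14)). Close under the proposed rule = max(D + 14, 28), taking Day 28 at its nominal date.

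| Days of therapy | Current close | Uncollected days before Day 28 | Share of 28 days | Proposed close |
|---|---|---|---|---|
| 3 (early stop) | Day 17 | 11 | 39% | Day 28 |
| 5 | Day 19 | 9 | 32% | Day 28 |
| 7 | Day 21 | 7 | 25% | Day 28 |
| 10 | Day 24 | 4 | 14% | Day 28 |
| 14 | Day 28 | 0 | 0% | Day 28 |
| 17 | Day 31 | 0 | 0% | Day 31 |
| 21 | Day 35 | 0 | 0% | Day 35 |

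The gap exists only below 14 days of therapy.

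**Illustration for deaths (assumptions, not trial data).** Assume a constant hazard and a 28-day mortality m of 16% to 60%, the range Section 4.2.1 cites for critically ill patients. Then h = −ln(1 − m)/28, and the probability of dying after the close but by Day 28 is exp(−h(D + 14)) − (1 − m).

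- D = 5: 0.048 (m = 0.16) to 0.137 (m = 0.60). Dividing by m, 30% to 23% of Day 28 deaths.
- D = 7: 0.037 to 0.103, or 23% to 17% of Day 28 deaths. If every subject had a 7-day course, that is 1.1 to 3.1 deaths among 30 and 0.6 to 1.5 among 15.

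These figures count all deaths after the close. Deaths that need no SAE report are a subset, because related deaths and deaths that are the outcome of an earlier SAE remain reportable.

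**The case against.** The strongest defence is that anchoring on exposure is a coherent choice. Every subject gets the same 14 days after the last dose, and a visit is added for long courses to secure it. Much is also protected:

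- **Toxicity that ends treatment is not dropped.** Section 5.8 keeps subjects stopped for liver criteria in all planned procedures, with bloods until values normalise. Footnote h and Section 7.1.3.1 follow laboratory AEs emerging on therapy until they resolve or stabilise. Sections 7.2 and 7.2.3.1 follow AEs and SAEs for outcome.
- **Tier 1 is not truncated.** Nephrotoxicity and both hepatic criteria are defined on laboratory values, and blood is drawn at Day 28. A late hepatic value could count as a Tier 1 event without a required ECI report, but that is a mismatch in notification and not an analysis error.
- **Tier 2 intervals are descriptive**, as Section 8.2.5.2 says.

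A reader might infer that the arms are compared over unequal windows. The documents do not show this. Allocation is blinded and stratified by infection type, which sets the minimum course. Assuming a constant hazard and a 30% 28-day event rate, a 5-day course yields 21.5% by Day 19 and a 21-day course 36.0% by Day 35, but that contrasts course lengths, not treatment groups. With assumed mean courses of 10 and 12 days, the same hazard gives 26.3% by Day 24 and 28.2% by Day 26.

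A reader might also see a contradiction between the Day 28 tick for AE monitoring and footnote h. The two can stand together: the Day 28 visit can collect events that arose between early follow-up and last dose + 14 days.

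All of this stands. It leaves untouched new-onset events after the close, unrelated deaths with no earlier SAE, and a window length that depends on treatment duration.

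**Conclusion.** The point holds as a worthwhile, inexpensive improvement to the collection of data for a primary safety objective. It is not a flaw that invalidates the comparison. Counted from randomisation, the window runs from about Day 17–21 after an early stop or minimum course to Day 35 after 21 days. At the two minimum durations, 9 or 7 of the first 28 days go uncollected for new, unrelated events.

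A reader might conclude that late deaths escape SAE reporting altogether or are lost. Neither is supported. Related SAEs are reportable whenever they come to light, and the date and cause of every death by Day 28 go on the survival eCRF. What remains is a difference in scope between the SAE and mortality tables, for which the plan gives no reconciliation rule.

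The day counts follow from the protocol alone. The mortality shares rest on a constant hazard and an assumed 28-day rate. They are also unfavourable cases: the 5-day minimum applies only to cIAI and cUTI, the 16% to 60% range comes from critically ill patients, and Section 4.2.2.5 reports colistin courses averaging about two weeks, where the gap is zero. The size and direction of any imbalance between arms cannot be derived from the documents.

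**What to change.** In Sections 7.1.2.6, 7.2, 7.2.3.1 and 7.2.3.2 and in flow-chart footnote h, end AE, SAE and ECI collection at the later of 14 days after the last dose of IV study therapy and the Day 28 visit. Leave the any-time rule for related SAEs as it is. Collection then closes no earlier than Day 28 for anyone followed that far, and courses with D + 14 beyond the Day 28 visit are unchanged.

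In Section 8.2.5.2, state the AE analysis period. Keep the summary to last dose + 14 days, and add a supplementary Group 1 versus Group 2 summary of AEs and SAEs over the common period from first dose to Day 28. This should not replace the exposure-anchored summary: a Day 28 cut-off would leave out events that occur later but still within 14 days of a long course.

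The cost is a wording amendment and one extra set of tables. No visit or sample is added, because the Day 28 review, examination and bloods are already scheduled. The downside is a few more late AE and SAE records, mostly unrelated to treatment.
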